

Item 4 Purpose and rationale Insert purpose, objectives and research questions/hypotheses here. If you cut and paste from another document, make sure the excerpted material answers the question
	
We propose a randomized, double-blind, sham-controlled, 20 consecutive day trial of adjunct TMS to the right DLPFC in active duty service members and veterans with PTSD receiving an integrated and evidence-based treatment (i.e. TAU) for PTSD incorporating both adequate pharmacological approaches and Cognitive behavioral therapy (CBT) at Laurel Ridge Treatment Center (LRTC). In addition to TAU, consented patients will be randomized to receive irTMS in one of two treatment arms: Arm 1 delivers active irTMS to the right DLPFC. Arm 2 delivers sham TMS (inactive coil) to the right DLPFC. To ensure equivalent placebo effects across arms, sham TMS delivers the exact sound produced during active irTMS, therefore patients are unable to discriminate between sham and active TMS. Moreover, clinicians providing TAU at LRTC and researchers conducting clinical outcomes assessments will be blinded to each participants' treatment arm. Resting-state fMRIs (rs-fMRIs) will be used both for treatment planning (baseline imaging), which guides the individualized positioning of the TMS coil, and to characterize TMS-induced network connectivity (imaging treatment week 3). Self-report scales will be done weekly at LRTC. A 1-month post-treatment clinical follow-up will be conducted in person or over the phone to evaluate maintenance of clinical outcomes. Considering that depressive symptomatology, often meeting diagnostic criteria Major Depressive Disorder (MDD), is commonly observed in patients with PTSD, patients with comorbid PTSD and MDD won't be excluded from the study and we will also assess depressive symptoms throughout treatment at the same time intervals—i.e., baseline, weekly, and 1 month post-treatment.
 
Aim 1. Test whether compared with TAU plus sham irTMS, TAU plus adjunct active irTMS is associated with greater clinical improvement that differs in specificity to PTSD or depressive symptomatology according to the targeting of right DLPFC .
 
 Hypothesis 1. TAU plus adjunct active irTMS to the right DLPFC will be superior to TAU plus sham irTMS in relieving PTSD symptoms. 
Aim 2. Test for irTMS-induced changes in network functionality (plasticity) using rs-fMRI.
 
 Hypothesis 2a. Intrinsic connectivity will be attenuated by active irTMS in networks connected to the respective treatment sites, as tested by correlation with the number of sessions received at the time of scanning and by pre-treatment-to-post-treatment contrast. Hypothesis 2b. Treatment-induced decreases in connectivity will correlate with symptom improvement within and across treatment arms.

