
Patients diagnosed by the LRTC with PTSD, receiving evidenced based combined pharmacological and psychotherapy (either PE or CPT)
	
 1) Male or female English-speaking active duty or recently retired veteran patients who have deployed post 9/11 receiving treatment at LRTC between the ages of 18-65 years; 2) Patients must have a diagnosis of PTSD confirmed by the Clinician-Administered PTSD Scale (CAPS-5) at screening, 3) Subjects must have a minimum PTSD Symptom Checklist for DSM-V (PCL-5) symptom severity rating of 25. 	
 1) Subjects with a diagnostic history of bipolar disorder, schizophrenia or schizoaffective disorder as documented in the medical record. 2) Substance use disorder during the 12 months prior to screening; except that Mild - Moderate, but not Severe, Alcohol Use Disorder (using DSM-5 criteria) will be allowed as determined by LRTC medical provider review. 3) Any history or signs of serious medical or neurological illness including seizure disorders. Except for seizures, a subject with a clinical abnormality may be included only if the study clinician considers the illness will not introduce additional risk and will not interfere with the study procedures. This will be determined during the screening phase via self-report and/or medical history review. 4) History of traumatic brain injury (TBI) with loss of consciousness for 20 minutes or more as determined by the History of Head Injuries questionnaire. 5) Females will be excluded if they are pregnant (i.e. positive pregnancy test identified after their LRTC intake). 6) Any history or signs of metal objects deemed unsafe for MRI or that may adversely affect image quality of the brain region (e.g. surgical clips, cardiac pacemakers, metal implants, etc.) in the body at the time of screening as indicated by self-report. MRI can have risks for persons with foreign bodies implanted in their body.

Item 6
Research Plan / Description of the Research Methods a. *Provide a comprehensive narrative describing the research methods.*
Provide the plan for data analysis (include as applicable the sample size calculation).

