Step-by-Step Methods: We propose to test 100 patients (i.e. 50 per arm) who meet criteria for PTSD as determined by the Clinician Administered PTSD Scale (CAPS-5) and the outlined study inclusion criteria. We anticipate consenting and screening approximately 200 male and female subjects, in order to meet the target enrollment goals. To account for subject dropouts and retain a sample of 100 subjects completing the double-blind treatment phase (50 per treatment group), 132 eligible subjects (66 in each group) meeting the study inclusion criteria will be randomized for the study. See also Table of Study Procedures below.

Recruitment

Patients will be recruited at LRTC from institution's PTSD inpatient program by the study staff supervised by the On-site Investigator's team. Upon admission to the LRTC, patients will be informed about this treatment trial by either their staff psychiatrist or a member of the LRTC's research team. Each patient will be given an information sheet describing the study. If interested in participating, each patient will be shown a video describing the treatment trial and each of the tools/treatments used throughout the study (i.e. MRI and TMS).

Pre-Screening and LRTC Intake

Under an IRB approved HIPAA Waiver of Authorization, Waiver of Informed Consent, and Waiver of Documentation of Informed Consent, study personnel will conduct a brief pre-screening intake interview where the basic study inclusion and exclusion criteria will be reviewed to help the individual determine if he or she meets the study criteria or has obvious exclusions from the study protocol. This information will be maintained as a secure file with the following information: name, phone number, name of study, referral date, referral source, potential eligibility status, reason if not eligible, and verbal permission to contact the caller in the future for other studies. Subjects who agree to study participation will sign a consent document before any further screening will take place. Any individually identifiable information and Protected Health Information (PHI) collected on individuals who do not consent to participation will not become part of the research data. If subjects agree to participate in the research, the identifiable data collected will become part of the subjects' research records and will be stored according to the research confidentiality plan.

Consent Process

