The right DLPFC treatment target locations will be based on connectivity strength with ACC and Precuneus using region-seeded resting-state BOLD fMRI. Coil orientation will be corrected for the underlying gyral anatomy, using a T1-MRI derived cortical surface model to align the E-field according to the cortical column cosine model. Stimulation intensity will be corrected for the distance of the stimulation site from the scalp/coil surfaces. Intensity ranges will be individually adjusted for each patient—to deliver depth-corrected E-fields between 80 volts/meter and 95 volts/meter.

Sham TMS: An image-guided treatment plan will be computed for sham TMS subjects in the same manner as for active irTMS to ensure therapist blinding.

irTMS Treatment Sessions. All participants will continue with their TAU at LRTC (or its treatment clinics) including regular medication management encounters with their attending psychiatrist and therapy sessions as of their treatment. An effort will be made to limit the disruptions in patients' TAU by working research assessments and irTMS around their expected TAU programming. irTMS treatment visits will take place at the LRTC starting as soon as possible after the treatment plan is completed, expected to be 1-2 working days following baseline scanning.

irTMS Position/Holding. For each subject, the coil pose will be pre-computed from structural and functional MRI and stored as an individualized treatment plan. Each subject's treatment plan will be registered to his/her head by creating a scalp model with a high-resolution digitizer, an integrated component of the irTMS system. In each arm,

the TMS coil will be positioned and held by the robot (under the treatment technician's supervision).

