3. Clinician-Administered PTSD Scale for DSM-5 (CAPS-5)		X						X
4. PTSD Checklist for DSM-5 (PCL-5)		X		X	X	X		X
5. Life Events Checklist - 5 (LEC-5)		X						X
6. Deployment Risk and Resiliency Inventory-2 (DRRI-2) Combat and Postbattle Experiences Subscales		X						
7. Patient Health Questionnaire-9 (PHQ-9)		X		X	X	X		X
8. 'Structured Interview Guide for the Montgomery-Åsberg Depression Rating Scale (SIGMA).pdf'		X				X		X
9. Generalized Anxiety Disorder Screen (GAD-7)		X		X	X	X		X
10. Alcohol Use Disorders Identification Test (AUDIT) self-report version		X						X
11. Quick Drinking Screen (QDS) self-report version		X						X
12. Fagerstrom Test for Nicotine Dependence		X				X		X

13. Fagerstrom Test for Nicotine Dependence – Smokeless Tobacco		X				X		X
14. Insomnia Severity Index (ISI)		X				X		X
15. Snoring, Tired, Observed, Blood Pressure (STOP) Sleep Apnea Screen		X						
16. Patient Reported Outcomes Measurement Information System (PROMIS) Sleep Disturbance and Sleep-Related Impairment short forms		X				X		X
17. Depressive Symptoms Index – Suicidality Subscale		X				X		X
18. Self-Injurious Thoughts and Behaviors Interview short form		X				X		X
19. Veterans RAND 12-Item Short Form Health Survey (VR-12)		X						X
20. Brief Inventory of Psychosocial Functioning (B-IPF)		X						X
21. Health Questionnaire		X				X		X
22. Clinical Global Impressions (CGI)		X				X		X
Adverse Events Monitoring			X	X-X	X-X	X-X		X
Concomitant Medications/Treatment	X-X	X-X		X-X	X-X	X-X		X
Structural MRI			X					
Intrinsic Connectivity by Blood-Oxygen-Level-Dependent Functional MRI			X				X	
Motor threshold assessment			X				X	
irTMS Treatment (20 consecutive days)				X-X	X-X	X-X		
Participant Blind Form							X	
Independent Evaluator Blind Form								X

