Discontinuation of Subjects. Subjects may be discontinued from study treatment and assessments at any time. Specific reasons for discontinuing a subject from this study are: 1) Voluntary discontinuation by the subject, who is at any time free to discontinue his/her participation in the study without prejudice to further treatment; 2) Clinical deterioration: The following are objective criteria for clinical deterioration, (a) a 25% increase in the PCL-5 at any time during the study, (b) Patients with a CGI-I score ≥ 6 at any post-baseline visit, and (c) the onset of active suicidality as assessed by the study clinicians requiring treatment outside of the study protocol; 3) Evidence of intolerable adverse reaction, or unable to tolerate iTMS or MRI; 4) Safety reasons as judged by the investigator.

Potential Benefits.

- The potential benefit to participants is the potential for PTSD and/or depressive symptom relief.

Adverse Events, Unanticipated Problems, and Deviations.

Adverse Events will be assessed and monitored according to the established STRONG STAR and CAP SOPs and the IRB of record's policies and procedures. Reporting Adverse Events, Unanticipated Problems Involving Risks to Subjects or Others (UPIRSOs), and Deviations to the Office of the IRB. All adverse events, unanticipated problems involving risk to subjects or others, and deviations will be reported to the Institutional Review Board (IRB) in accordance with current IRB policy. UPIRSOs and recurrent non-compliance with study procedures will be reported promptly to the IRB. All adverse events that do not meet the UPIRSO criteria and deviations that are not non-compliance will be summarized at Continuing Review per the IRB of record's policy.

Research Monitor.

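### The CGI-I stopping rule has no scheduled rating in Weeks 1 and 2: the first post-baseline CGI is on Day 20, after about 13 to 20 of 20 sessions

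*Combined protocol and SAP*

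**What the plan says.** Discontinuation of Subjects (Item 6) gives three objective criteria for clinical deterioration: (a) a 25% rise in the PCL-5, (b) "Patients with a CGI-I score ≥ 6 at any post-baseline visit", and (c) new active suicidality as assessed by study clinicians. Meeting one can end both study treatment and assessments.

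The Table of Study Procedures sets the timing. Row 22, the CGI, is marked at Baseline, Week 3 (Day 20) and follow-up. Row 4, the PCL-5, is marked at Baseline, Days 7, 14 and 20, and follow-up; the PHQ-9 and GAD-7 follow the same pattern. Item 4 agrees: "Self-report scales will be done weekly at LRTC". Adverse-event and concomitant-treatment monitoring are also marked in Weeks 1, 2 and 3.

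Risk Minimization adds that experienced study clinicians are available during sessions, that every subject is seen weekly for behavioral symptoms, and that a subject whose condition worsens significantly is withdrawn from the protocol.

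**The concern.** The rule is worded for every visit after baseline, but at the first two of those visits no CGI is planned. An unscheduled rating is not forbidden, yet nothing in the protocol calls for one. A site that follows the table will therefore not apply criterion 2(b) until treatment is nearly over, when stopping irTMS spares the participant little.

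None of the clinician-administered instruments (CAPS-5, MADRS interview, self-injury interview, CGI) is marked at Day 7 or Day 14. The numeric deterioration rule that can act on scheduled data in those weeks is the PCL-5 rule, and it has a ceiling for participants who start with high scores.

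**Working it through.** The plan does not state how many sessions precede the first CGI, so there is no figure to reproduce. The check has three parts.

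**1. Schedule.** The eight columns are Intake, Baseline, MRI (Day 2-3), Day 7, Day 14, Day 20, Post-Treatment (Day 21-24) and follow-up. The CGI row has three marks (columns 2, 6, 8). The PCL-5 row has five (columns 2, 4, 5, 6, 8). The two extra marks are Days 7 and 14, so the difference is not a matter of column alignment.

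**2. Sessions given by each visit.** Inputs:

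- The scan is on Day 2-3 (Table of Study Procedures).
- Treatment start is "expected to be 1-2 working days following baseline scanning" (irTMS Treatment Sessions).
- Sessions run daily, up to 20 (irTMS Treatment Protocol).

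With the first session on day *s*, the number given before day *d*'s own session is *d* − *s*, and 20 − (*d* − *s*) remain. Without a weekend, *s* runs from 2 + 1 = 3 to 3 + 2 = 5. The latest start is a Friday scan on Day 3 plus two working days, which is Tuesday, Day 7. If the table's days are treatment days, *s* = 1.

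| First session | Before Day 7 | Before Day 14 | Before Day 20 | Left at Day 7 / 14 / 20 |
|---|---|---|---|---|
| Day 3 | 4 | 11 | 17 | 16 / 9 / 3 |
| Day 5 | 2 | 9 | 15 | 18 / 11 / 5 |
| Day 7 | 0 | 7 | 13 | 20 / 13 / 7 |
| Day 1 | 6 | 13 | 19 | 14 / 7 / 1 |

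Counting the Day 20 session adds one, so the full range is 13 to 20 of 20. The central case is 15 to 17 (75% to 85%).

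The total of 20 sessions is taken from the abstract's methods, the irTMS Treatment Protocol and the table. The protocol also gives 24,000 pulses in all, which is 24,000 / 1,600 = 15 sessions. That is a separate inconsistency, and nothing here rests on pulse totals.

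**3. Reach of the PCL-5 rule.** The scale has 20 items scored 0 to 4, so the maximum is 20 × 4 = 80. Entry requires a minimum "symptom severity rating of 25" (Item 5). If the 25% is taken from baseline:

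- 64 × 1.25 = 80, which is just attainable.
- 65 × 1.25 = 81.25, which exceeds 80.

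Baselines of 65 to 80 therefore cannot meet the rule. That is 16 of the 56 possible eligible scores (25 to 80).

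The protocol does not name the reference point. If it were the previous assessment, a run of 70, 50, 65 would qualify (65 / 50 = 1.30), and the ceiling would not apply in that form.

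**The case against.** The strongest reply is that a much-worse participant would be noticed without a scheduled CGI. Participants come from an inpatient program and are treated while hospitalized. Study clinicians are available during sessions, which run seven days a week. Adverse events are monitored, attending psychiatrists see participants, and the Research Monitor can remove a subject. Suicidality, intolerance and investigator judgement are all grounds for stopping, and significant worsening leads to withdrawal on any day. This stands. A reader might infer from row 22 that deterioration goes unwatched until Day 20; the documents do not support that.

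A second reply is that the rule and the table do not contradict each other, because 2(b) says what happens when a score of 6 or more is recorded and does not promise a rating at each visit. This also stands: it is a design choice with a gap, not an internal contradiction.

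A third is that the PCL-5 ceiling is a weakness of criterion (a) and depends on an unstated reference point. It is fair to require that condition. It is also wrong to read 16 of 56 scores as a proportion of participants.

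What survives is narrower. The withdrawal for significant worsening names neither instrument nor cut-off, and the weekly contact names no scale. The protocol's own numeric clinician threshold has no scheduled data in Weeks 1 and 2.

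**Conclusion.** The concern holds in limited form. It is certain from the table that no CGI is scheduled at Day 7 or Day 14 and that the first post-baseline one is on Day 20. On every reading of the day numbering that is late in treatment, with at least 13 of 20 sessions (65%) given. The narrower 15 to 17 assumes a Day 3-5 start, no weekend delay, and the Day 20 session not counted.

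The safety consequence is modest and cannot be put as a number of participants. It is greatest for those with a baseline PCL-5 of 65 to 80, on the assumption that the 25% rise is measured from baseline; the documents do not say how many that will be. The change is worth making because it is cheap and lets a stated rule act while most or much of the treatment can still be stopped.

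**What to change.** 1. In row 22 of the Table of Study Procedures, mark a brief CGI-I by a blinded clinician at the Week 1 (Day 7) and Week 2 (Day 14) contacts. Item 4 already provides that "clinicians providing TAU at LRTC and researchers conducting clinical outcomes assessments will be blinded", so the rating fits the existing blind.
2. In all the clinical-deterioration criteria under Discontinuation of Subjects, and in the matching withdrawal sentence in Risk Minimization (measure 4), state that deterioration stops irTMS while PCL-5 and CAPS-5 assessments continue where the participant agrees. Changing 2(b) alone would leave it in conflict with measure 4 and treat deterioration differently by criterion.

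**Gain.** For a Day 3-5 start, 2(b) could act with 16 to 18 sessions left at Day 7 and 9 to 11 at Day 14, against 3 to 5 at Day 20. With a Day 7 start, the Day 7 rating adds nothing and 13 sessions remain at Day 14.

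**Cost.** The plan is that "132 eligible subjects (66 in each group) meeting the study inclusion criteria will be randomized for the study", so the upper limit is 132 × 2 = 264 short ratings. They are a new task at contacts that now carry only self-report scales among the rating instruments, but they need no extra visit and no change in sample size.

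A few participants may stop treatment earlier. If 1% to 5% did (an assumption; the documents give no rate), that is 132 × 0.01 = 1.3 to 132 × 0.05 = 6.6 people, or 4% to 21% of the dropout allowance of 132 − 100 = 32. Part 2 of the fix limits the resulting loss of outcome data in the PCL-5 mixed model to those who decline further assessment.

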Methods: Consented participants receiving TAU for PTSD at LRTC will be randomized to receive 20 consecutive days of adjunct iTMS according to one of these two treatment arms: **Arm 1** TAU plus iTMS to the right DLPFC or **Arm 2** TAU plus sham iTMS to the right DLPFC. At UTHSCSA's Research Imaging Institute (RII), where all brain imaging and motor threshold assessments will be conducted, iTMS treatment plans will be generated based on (pre-treatment) anatomical and functional magnetic resonance imaging (fMRI) to guide the optimal robotic positioning of the TMS coil to accurately target each subject DLPFC. Participants will be assessed at baseline, during treatment, immediately following treatment and at 1-month post-treatment. A comparison of baseline brain connectivity measurements with subjects' fMRI conducted immediately following treatment will be conducted to identify network connectivity changes potentially associated to treatment response.

Clinical Relevance: This will be the first study to determine the clinical effects of adjunct iTMS delivered to the right DLPFC in the treatment of PTSD, to provide clues about the ideal neural networks to target for more robust clinical outcomes, and to identify potential biomarkers of treatment response including changes in brain networks connectivity.

Item 3 Background	
--------------------------	--

Describe past experimental and/or clinical findings leading to the formulation of your study.

For research involving unapproved drugs, describe animal and human studies.

For research that involves approved drugs or devices, describe the FDA approved uses of this drug/device in relation to your protocol.

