Phase I: Baseline MRI. Once the participant has completed the psychological assessments required to determine inclusion/exclusion criteria, eligible participants will be taken from the LRTC to the Research Imaging Institute (RII) at UTHSCSA. When the participant arrives, the participant will undergo an anatomical and functional magnetic resonance imaging (MRI) session. Earplugs will be provided at every MRI session. MRIs use strong magnets and radio waves to non-invasively acquire images of organs and tissues. Unlike X-rays, MRIs do not expose subjects to radiation, therefore it is considered safe to obtain many MRIs in a single scanning session or over multiple days; the initial MRI scans may take up to 2 hours. In the event that the participant cannot tolerate the MRI procedure, they will be withdrawn from the study. Participants will be imaged at the RII using a research-dedicated 3T Siemens TIM/Trio MRI scanner (Siemens, Erlangen, Germany) with an eight-channel phased array coil. Structural imaging will be obtained only once, upon enrollment. Structural images will be used for iTMS treatment planning (described below) and for spatial normalization to a standard anatomical template. MRI images will be obtained two times (i.e. pre-treatment and post-treatment) and used to detect symptom-specific network abnormalities and treatment-induced plasticity. We will also perform motor threshold assessments for each patient (at pre-treatment and post-treatment, immediately after each MRI) to determine the correct intensity and train durations needed to safely deliver iTMS in each patient's 3-Week Treatment Phase. The post-treatment motor threshold assessment are important to the future establishment of safety guidelines for iTMS treatment of PTSD.

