robust and widely used pulse sequence for intrinsic connectivity modeling. BOLD images will be used for computing treatment plans and for testing for intrinsic connectivity changes by symptom score and with treatment. BOLD data will be acquired as 360 whole-brain volumes acquired with a TR = 2500 ms, TE = 30 ms, tip angle = 90°, 128 x 128 voxels, 1.7 mm x 1.7 mm, and 36 slices (4.0 mm thickness). This sequence requires ~ 15 minutes. Resting-state BOLD (15-min acquisition) will be used to map per-subject the voxel-wise intrinsic connectivity of DLPFC with the anterior cingulate cortex (ACC) and Precuneus; this will guide aiming parameters.

Motor Threshold Assessment. After the baseline MRI session, each patient will undergo a brief motor threshold assessment by single pulse TMS to their primary motor cortex hand region which elicits a contraction of the targeted hand muscle. The motor threshold assessment begins by locating the hand region and applying single pulses of TMS—with at least 5 seconds between successive pulses—at increasing levels of TMS intensity. We continue to ramp up the TMS intensity with each TMS pulse until we observe a contraction of the targeted hand muscle in 5 out of 10 pulses at a given TMS intensity. This TMS intensity will then be recorded as that patient's resting motor threshold. Using the patient's BOLD fMRI of the primary motor cortex, we can calculate their coil-to-cortex depth and use this information to determine the correct irTMS treatment intensity for the DLPFC and also determine the correct train duration needed to safely deliver 20Hz irTMS in each patient using published safety guidelines on appropriate train durations at specific TMS frequencies and intensities.

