Intrinsic Connectivity by BOLD fMRI. Data will be analyzed using FSL's FEAT program. Head movements are corrected by affine registration using a 2-pass procedure. BOLD data will be normalized to MNI space single-patient template using the "unified segmentation" approach, followed by a 5-mm full width at half maximum Gaussian smoothing. Spurious correlations with nuisance variables are removed using a recently validated framework. Data are band-pass filtered preserving frequencies between 0.01 and 0.08 Hz. The time course of each seed region's BOLD signal will be extracted as the first eigenvariate of activity in all gray-matter voxels located within the respective cluster. To quantify resting-state functional connectivity linear (Pearson) correlation coefficients between the time series of the seeds (targeted DLPFC nodes of each patient's DLPFC-limbic and DLPFC-motor networks) and any other gray matter voxel will be computed. Voxel-wise correlation coefficients will be transformed into Fisher's Z-scores (with non-sphericity correction). These images will be used for iTMS treatment planning. The resting-state fMRI scan will also be used to assess, network-specific functional connectivity differences between each patient's pre-treatment and post-treatment scans.

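### Hypothesis 2a credits active irTMS with reduced connectivity, but the plan specifies no active-versus-sham comparison of connectivity change

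*Combined protocol and SAP*

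**What the plan says.** Item 4, Hypothesis 2a: "Intrinsic connectivity will be attenuated by active irTMS in networks connected to the respective treatment sites". The same sentence gives the tests: correlation with the "number of sessions received at the time of scanning and by pre-treatment-to-post-treatment contrast".

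Item 2, Methods, describes the imaging comparison in the same terms: "A comparison of baseline brain connectivity measurements with subjects' fMRI conducted immediately following treatment will be conducted to identify network connectivity changes". Item 6, Intrinsic Connectivity by BOLD fMRI (in the Neuroimaging Data Analysis Plan), says the resting-state scan will be used to assess "network-specific functional connectivity differences between each patient's pre-treatment and post-treatment scans". None of these places mentions the sham arm.

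Four other parts of Item 6 bear on the point:
- Phase I: Baseline MRI provides for two MRI sessions per participant, one before and one after treatment.
- irTMS Treatment Sessions has every participant continue TAU, including medication management and therapy.
- Sham TMS has a treatment plan computed for sham participants in the same way as for active ones.
- irTMS Treatment Protocol gives daily treatment while the participant is hospitalised, to a maximum of 20 sessions.

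**The concern.** Hypothesis 2a is a causal statement about active stimulation, but its two tests are before/after comparisons. Participants are in an intensive PTSD programme with psychotherapy and medication, and connectivity may change over three weeks without any stimulation. The randomised sham arm exists to absorb such changes, yet the plan does not say it will be used for that purpose in Aim 2.

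Followed as written, the plan could report attenuation by active irTMS when the sham arm had changed by the same amount. Hypothesis 2b then correlates decreases that it calls treatment-induced with symptom improvement, so it inherits the attribution.

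**Working it through.** **Is an arm comparison specified elsewhere?** Three places come close.
- Hypothesis 2b refers to the arms, separately and together, but it correlates connectivity decrease with symptom improvement. It does not test whether the decrease differs by arm.
- Item 6, on BOLD fMRI for computing treatment plans, mentions testing connectivity change by symptom score and with treatment. It defines no contrast.
- The Structural MRI paragraph of the Neuroimaging Data Analysis Plan mentions group-wise analyses, as the reason for spatial normalisation. It defines no contrast either.

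The mixed-effects models appear in the Clinical Outcomes Data Analysis plan, for the symptom scores.

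**Does session count separate stimulation from time?** Every participant has count 0 at the first scan. Over both scans, with mean m and variance v of the count at the second, the correlation of session count with a pre/post indicator is m / √(m² + 2v).
- Counts spread evenly over 16 to 20 (assumed): m = 18, v = 2, giving 18/√328 = 0.99.
- Counts spread evenly over 10 to 20 (assumed): m = 15, v = 10, giving 15/√245 = 0.96.
- All at 20: 1.00.

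Session count is then almost a relabelling of pre/post. If the correlation is taken across participants at the second scan only, the count depends partly on length of stay, and so on how much TAU was received.

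**Size of the problem.** The documents give no alpha, power, SD or effect size for Aim 2, so there is no stated figure to reproduce. The only design input is 50 completers per arm (Item 6, Step-by-Step Methods). Assumed inputs are 50 usable scan pairs per arm, a two-sided 0.05 test, unit SD at each scan, scan-rescan correlation r, no stimulation effect, and a shift s common to both arms.

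The SD of change is √(2(1 − r)), which is 0.775 at r = 0.7. The noncentrality of the paired t test is s√50 / 0.775, or 0.91, 1.83 and 2.74 for s = 0.1, 0.2 and 0.3. The chance of a significant active-arm pre/post test (noncentral t, 49 df) is:

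| r | s = 0.1 SD | s = 0.2 SD | s = 0.3 SD |
|---|---|---|---|
| 0.5 | 10.7% | 28.4% | 54.8% |
| 0.7 | 14.6% | 43.3% | 76.6% |
| 0.9 | 34.1% | 87.3% | 99.6% |

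In simulation at r = 0.7, the baseline-adjusted active-versus-sham test rejected in about 5% of trials for each of these shifts, because a common shift cancels.

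**Price of the between-arm test.** Detectable differences at 80% power, 50 per arm, one connectivity measure:
- Within-arm at r = 0.7: about (1.96 + 0.84) × 0.775/√50 = 0.31 SD.
- Between-arm, baseline-adjusted: the residual SD is √(1 − 0.49) = 0.714, so about 2.80 × 0.714 × √(2/50) = 0.40 SD.
- The same pair is 0.40 and 0.49 SD at r = 0.5, and 0.18 and 0.25 SD at r = 0.9.
- If two regions are tested with Holm adjustment, the stricter step (alpha 0.025) needs about 0.45 SD between arms at r = 0.7.

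**The case against.** The strongest reply is that the trial is randomised and sham-controlled, that Hypothesis 2b and the mention of group-wise analyses show both arms in view, and that nothing confines the pre/post contrast to the active arm. On this reading the plan is under-specified, not committed to a within-arm test. That much stands, and it limits the claim to a comparison that is not specified. It does not remove the gap: a pre/post contrast pooled over both arms would not isolate stimulation either.

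The shift sizes and the scan-rescan correlation are assumptions. A common shift would mimic attenuation only if it were downward, and the documents give no direction. That also stands.

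A reader might infer two stronger points that the documents do not support.
- **Regression to the mean.** The target is chosen on baseline connectivity with the ACC and Precuneus ("map per-subject the voxel-wise intrinsic connectivity of DLPFC with the anterior cingulate cortex (ACC) and Precuneus; this will guide aiming parameters"), so a spurious drop on rescanning might be expected. This applies only if the outcome uses those same connections, and no outcome network is named. The number of candidate sites, their correlations and the direction of selection are not given either. The size and direction are unknown, so it is a caveat only.
- **Wrong seeds.** The analysis section takes its seeds as "seeds (targeted DLPFC nodes of each patient's DLPFC-limbic and DLPFC-motor networks) and any other gray matter voxel will be computed", and the DLPFC-motor label has no counterpart in the rule for choosing the target. But the text goes on to assign those images to treatment planning and mentions the pre/post use separately, and the ACC can fairly be called limbic. An effect on Aim 2 is therefore an inference. The label needs clarifying and no more.

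**Conclusion.** The concern holds in this form: no active-versus-sham comparison of connectivity change is specified for Hypothesis 2a, and neither stated test can separate stimulation from time or TAU. With no stimulation effect, a common shift of 0.1 to 0.3 SD would make the active-arm pre/post test significant in about 15% to 77% of trials at scan-rescan correlation 0.7 (11% to almost 100% over correlations 0.5 to 0.9), against about 5% between arms. These rates illustrate the exposure. They do not predict this trial, because only the 50 per arm comes from the documents.

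The documents do not show that the sponsor intends to ignore the sham arm. The point concerns a mechanistic aim and leaves the PCL-5 and CAPS-5 analyses untouched. It should be corrected, because an Aim 2 conclusion about active stimulation depends on it.

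**What to change.** In Hypothesis 2a and in Item 6, Intrinsic Connectivity by BOLD fMRI:
- Base the Hypothesis 2a conclusion on the active-versus-sham difference in post-treatment connectivity, adjusted for baseline connectivity.
- Use the same seed rule in both arms and at both scans, placed at each participant's stored right DLPFC target. The present extraction ("extracted as the first eigenvariate of activity in all gray-matter voxels located within the respective cluster") can be kept.
- Report within-arm pre/post contrasts and the session-count correlation as descriptive.
- Explain or remove the DLPFC-motor label.

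Because targets are chosen by the same rule in both arms, the between-arm comparison also removes any regression to the mean.

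The cost is rewording. Both scans, and a treatment plan for sham participants, are already provided for. The downside is sensitivity: about 0.40 SD detectable instead of 0.31 SD at scan-rescan correlation 0.7, or 0.45 SD if the sponsor tests two regions with Holm adjustment. The choice of regions and of seed size can stay with the sponsor, provided it is fixed before unblinding.
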